7.3.3.3. Prohibited Medications

Prohibited medications include any oral vancomycin, metronidazole, fidaxomicin, rifaximin, nitazoxanide, bezlotoxumab, or IVIG through the 8-week follow-up assessment unless newly prescribed by a treating investigator during the course of the study as a result of recurrent CDI diagnosis. Use of IVIG for treatment of a non-CDI indication is allowed. Use of non-dietary probiotics from Screening through 8 weeks after receiving the last study enema (including OTC and prescription) is also prohibited. Medication information will be collected at the Screening visit and changes in medications will be recorded throughout the study.

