7.5. Management of Treatment Failure

Following treatment, subjects meeting the protocol definition of treatment failure (**Section 7.3.6**) may be scheduled for administration of a second RBX2660 enema within 21 calendar days of failure determination. To receive the second RBX2660 enema, the site must provide documentation of meeting all treatment failure criteria as defined in **Section 7.3.6**. If the definition of treatment failure is not met, a second study treatment of RBX2660 will not be provided.

Treatment failures are required to be entered in the study database shortly after determination of failure to allow for sponsor awareness and assurance that a second study treatment of RBX2660 can be provided if requested.

The use of antibiotics prior to a second RBX2660 enema is at the discretion of the investigator. If antibiotics are given to control symptoms, a 24-72 hour washout period prior to administration of a second RBX2660 enema is required. If the subject will have a second enema, it needs to be administered within 21 calendar days of failure determination.

If a subject receives a second RBX2660 enema, follow-up is completed via telephone assessments at 1-week, 4-weeks, 8-weeks, and 6 months after the second study treatment of RBX2660.

Treatment failures who do not receive a second RBX2660 enema will continue to follow their original schedule of assessments for the duration of the study based on the first study enema.

If a subject has a treatment failure after receiving a second study treatment of RBX2660, the subject should be treated per the investigator's discretion.

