5.2 Time Point Algorithms

5.2.1 *Relative Day*

The date of study enema administration will be considered relative day 1, and the day before study enema administration will be relative day -1. Relative days will be calculated as follows only when the full assessment date is known (i.e., partial dates will have missing relative days, unless imputation methods have been specified):

For days before first enema:

Date of Assessment – Date of first enema administration

For days on or after first enema:

Date of Assessment – Date of first enema administration +1

For the purpose of statistical analysis, the analysis visit windows will be calculated in terms of study days since the day of the study enema administration, as illustrated in the following tables:

Table 1. Analysis Windows for Clinical Visits

Visit	Scheduled Study Day	Visit Window in Protocol (Days)	Visit Window for Analysis (Days)
Screening Visit	-20 through -1	-20 through -1	-20 through -1
Baseline/1 st Enema	1	1	1
1-week Office	8	5 - 11	5 - 11
8-weeks Office	57	54 - 60	54 - 60

Table 2. Analysis Windows for Phone Assessments

Visit	Scheduled Study Day	Visit Window in Protocol (Days)	Visit Window for Analysis (Days)
4-weeks - Phone	29	26 - 32	26 - 32
4 months - Phone	121	106 – 134	106 – 134
6 months - Phone	181	166 – 194	166 – 194

Table 3. Analysis Windows for Adverse Event Reporting by Onset Interval

Onset Interval Name	Onset Interval Analysis Window	Window for Analysis (Days)
Baseline	Screening - < Baseline	≤ -1
1-week	Baseline - 1-week	1 through 8
4-week	> 1-week - 4-week	9 through 29
8-week	> 4-week - 8-week	30 through 57
0-8-week	Baseline - 8-week	1 through 57
4-month	> 8-week - 4-month	58 through 121
6-month	> 4-month - 6-month	122 through 180+
8-week-6-month	> 8-week - 6-month	58 through 180+

If a subject has more than one assessment occurring in the same visit window, the data from the visit closest to the scheduled study day will be used for analysis. If two visits have the same distance from the scheduled study day, i.e., one visit occurs -1 day from study day, and the other visit occurs +1 day from study day, the data from the visit after the scheduled study day will be used for analysis.

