6.6 Safety Analysis

The SP will be used to summarize all adverse event data, unless otherwise specified. Safety data will be summarized for events after the first and second enemas, as well as combined. Events occurring after the first enema will be counted up to the date of retreatment, or study exit. Events on, or after, the date of a second enema will be assigned to the second period. The combined analysis will consider all events, after first enema through study exit, even if a subject receives a second enema.

6.6.1 *Analyses Supporting the Primary Safety Endpoint*

Assessment of the primary safety objective will include descriptive statistics and be performed on the SP. Additional sub-analyses of safety data may be performed on sub-populations.

6.6.2 *Other Safety Analyses*

6.6.2.1 *Adverse Events*

A summary of adverse events, TEAEs, non-serious TEAEs, and serious TEAEs will be summarized using counts of the number of events and frequencies (counts and percentages) of

the number of subjects. The incidence of each preferred term (PT) within the primary system organ class (SOC) as well as overall primary SOC incidence will be presented. Summaries may also be presented by PT, irrespective of SOC. A subject with multiple events coded to the same PT within a primary SOC will be counted only once for the PT within the primary SOC. Likewise, a subject with multiple events coded to the same SOC will be counted only once within the SOC.

An overall summary of AEs will present the incidence of (1) all TEAEs, (2) TEAEs related to IP, (3) TEAEs related to enema procedure, (4) TEAEs related to *C. difficile* disease, (5) TEAEs related to a preexisting condition, (6) serious TEAEs, (7) serious TEAEs related to IP, (8) serious TEAEs related to the enema procedure, (9) serious TEAEs related to *C. difficile* disease, (10) serious TEAEs related to a preexisting condition, and (11) TEAEs leading to death.

Frequency of occurrence and number and percent of subjects experiencing an event through 6 months follow-up will be presented for both the first and second enemas as follows:

- All TEAEs
- TEAEs by maximum severity
- TEAEs by relatedness to IP
- TEAEs by relatedness to *C. difficile* disease
- TEAEs by relatedness to enema procedure
- TEAEs by relatedness to preexisting condition
- TEAEs resulting in subject withdrawal
- TEAEs resulting in death
- Serious TEAEs
- Serious TEAEs by maximum severity
- Serious TEAEs by relatedness to IP

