6.8 Other Endpoints Analyses

Additionally, the other analyses will be conducted on other populations or subgroups as needed.

6.8.1 *Comparison of Baseline characteristics in subjects with treatment success with one dose of RBX2660 vs. those who were unsuccessful.*

A multivariate analysis or regression analysis will be used to identify predictors (if any) for subject success with one RBX2660 dose vs. those who were unsuccessful, for example, age or number of prior CDI events.

6.8.2 *Subject fecal microbial composition at Screening, 1-week, 4-weeks, 8-weeks, 4 months, and 6 months after study treatment.*

Descriptive statistics will be used to present the changes from Screening fecal microbial composition to those at 1-week, 4-weeks, 8-weeks, 4 months, and 6 months after study treatment for those subjects treated with RBX2660.

6.8.3 *Cdiff32 scores at Screening, 1-week, 8-weeks, 4 months, and 6 months.*

Changes from Screening in the Cdiff32 scores will be summarized using descriptive statistics. Last observation carried forward (LOCF) will be used to impute missing post-Baseline data. No inferential statistics will be performed.

6.8.4 *Recurrence of CDI within 8 weeks of second RBX2660 treatment in subjects.*

Determine the treatment success rate of those subjects who received two doses of RBX2660. This success rate will be calculated at 8 weeks following the second RBX2660 enema.

6.8.5 *Concentration of vancomycin-resistant enterococci in stool samples for subjects who were carriers at Baseline.*

Lab generated values for the presence of vancomycin resistant enterococcus based on submitted stool samples at Baseline and at 1-week, 4-weeks, 8-weeks and 4 and 6 months will be assessed for all subjects to identify any trends in the clearance of vancomycin-resistant enterococci following enema treatment.

6.8.6 *Presence of *C. difficile* in stool samples at Screening, 1-week, 4-weeks, 8-weeks, 4 months, and 6 months after study treatment.*

Lab generated values for the presence of *C. difficile* based on submitted stool samples at Baseline and at 1-week, 4-weeks, 8-weeks, 4 months, and 6 months will be assessed for all subjects to identify any trends in the clearance of *C. difficile* following enema treatment.

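### The stool analyses of C. difficile, VRE and microbial composition do not separate samples taken after rescue CDI anti-infectives or a second enema, so their trends mix several treatments

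*SAP*

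**What the plan says.** Three exploratory analyses in SAP 6.8 follow stool through 6 months:

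- 6.8.6: C. difficile results "based on submitted stool samples at Baseline and at 1-week, 4-weeks, 8-weeks, 4 months, and 6 months will be assessed for all subjects".
- 6.8.5: VRE values "will be assessed for all subjects to identify any trends in the clearance of vancomycin-resistant enterococci following enema treatment".
- 6.8.2: change in composition from Screening, "after study treatment for those subjects treated with RBX2660".

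None of these names a cut-off, exclusion or stratum for rescue treatment, and SAP 7.3 (missing data) adds none. On timing, SAP 5.2.1 defines relative day on or after treatment as "Date of Assessment – Date of first enema administration +1" and states that "the analysis visit windows will be calculated in terms of study days since the day of the study enema administration".

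Rescue is part of the design. Protocol 7.3.3.3 bars the listed CDI anti-infectives through the 8-week assessment "unless newly prescribed by a treating investigator during the course of the study as a result of recurrent CDI diagnosis". Protocol 7.5 allows a second enema after a failure and otherwise says: "Treatment failures who do not receive a second RBX2660 enema will continue to follow their original schedule of assessments". Protocol 10.4 requests optional stool at 1, 4 and 8 weeks and 6 months after a second enema.

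For safety data the SAP does draw a line. Section 6.6 says: "Events occurring after the first enema will be counted up to the date of retreatment, or study exit".

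**The concern.** SAP 2.3 objectives 3, 5 and 6 ask how the flora changes and whether VRE and C. difficile clear after RBX2660. A treatment failure needs a positive central-laboratory C. difficile test (Protocol 7.3.6). A subject who fails, takes oral vancomycin or another listed drug, and is negative at month 4 would then count toward clearance following enema treatment. The same antibiotics can act on the flora measured for VRE and composition. The late part of each trend could therefore describe a sequence of treatments while being read as the effect of one enema.

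**Working it through.** The plan has no figure to reproduce. SAP 3.3 gives no powering, and SAP 6.8.6 looks for trends without defining a clearance proportion.

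**Step 1. Which post-rescue samples land in first-enema windows?** The SAP gives no window for stool as such, so I take each sample to inherit the window of its contact (SAP Tables 1 and 2): days 5-11, 26-32, 54-60, 106-134 and 166-194.

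*Failures given antibiotics only.* They stay on the original schedule, so every later scheduled sample falls in a first-enema window.

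*Retreated failures.* Let the second enema fall on first-enema day s. I take s from 3 (two days of symptoms are needed) to 57 + 21 = 78. A sample d days later falls on day s + d, which lies in the window lo to hi when lo − d ≤ s ≤ hi − d.

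- 4-month window: the 8-week sample (d = 56) enters for s = 106 − 56 = 50 to 134 − 56 = 78.
- 8-week window: the 1-week sample enters for s = 47-53, the 4-week sample for s = 26-32 and the 8-week sample for s = 3-4.
- 6-month window: the 6-month sample (d = 180) enters for s = 3 to 194 − 180 = 14, or up to about 28 if taken 14 days early.

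Of the 76 possible days for s, an on-target post-second-enema sample enters the 8-week window on 16, the 4-month window on 29 and the 6-month window on 12. Mixing is complete for antibiotic-only rescue and partial for retreated subjects.

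**Step 2. Size for C. difficile.** Let f be the failure share, r the share of failures negative after rescue, and q clearance among non-failures.

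- All samples: (1 − f)q + f·r
- Confirmed recurrence counted as not cleared: (1 − f)q
- Difference: f·r

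The values of f come from Protocol 5.3: 100 − 78.9 = 21.1% (2015-01), 100 − 70.4 = 29.6% (2017-01) and 16/32 = 50.0% (2013-001, first enema). The documents give no r, so I assume 0.25 to 1.0.

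| Source of f | f | f·r at r = 0.25 | f·r at r = 1.0 |
|---|---|---|---|
| 2015-01 (two-enema treatment) | 21.1% | 5.3 points | 21.1 points |
| 2017-01 | 29.6% | 7.4 points | 29.6 points |
| 2013-001, first enema | 50.0% | 12.5 points | 50.0 points |

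These figures assume that Baseline-positive subjects fail at the quoted rates and that every failure supplies a later sample.

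**Step 3. Three conventions on one example.** Take f = 0.296, an assumed q = 0.90 and r = 0.786. That r is 11/14 from 2013-001, a clinical success rate after a second enema, used only as an illustration.

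- All samples: 0.704 × 0.90 + 0.296 × 0.786 = 86.6%
- Confirmed recurrence as not cleared: 0.704 × 0.90 = 63.4%
- Post-rescue samples dropped: only non-failures remain, so 90.0%

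**The case against.** A reader might infer that the analyses overstate clearance because they fail to stop at rescue. Step 3 shows otherwise: dropping post-rescue samples moves the example from 86.6% up to 90.0%. The upward bias exists only against the convention that a confirmed recurrence is not cleared. Much of the gap is that convention itself. If no failure submitted a later sample, the comparison would be 90.0% against 63.4%, or 26.6 points, with no rescue clearance counted at all. This stands, and it limits what the f·r range can show.

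A reader might also infer that the plan credits rescue clearance to the first enema. SAP 6.8 speaks only of enema treatment and study treatment, and the documents call the second enema a study treatment too. The link to the first enema comes from the day count in SAP 5.2.1. Second-enema follow-up also has its own column in the schedule, so an analyst working by nominal visit could keep those samples apart.

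For VRE and composition, nothing in the documents shows which way rescue would move the result.

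The SAP 6.6 precedent is partial. It splits adverse events at retreatment, not at antibiotics, and keeps a combined analysis as well. An all-sample summary is a legitimate description of what happens under the whole treatment policy. The samples are optional, the endpoints are descriptive, and SAP 6.8 leaves room for further analyses as needed.

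These arguments reduce the claim. They do not supply the missing rule: SAP 6.8 still says nothing about how post-rescue samples are to be handled or labelled.

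**Conclusion.** The point holds as a minor gap in the SAP. As written, the three stool trends combine first-enema, rescue-antibiotic and second-enema effects. For C. difficile, the all-sample figure exceeds one that counts confirmed recurrence as not cleared by f·r, about 5 to 30 points for f of 21% to 30% and r of 0.25 to 1.0. That range is an illustration. Its r is assumed, its lower f comes from a two-enema study, it assumes full sampling of failures, and the first-enema rate in 2013-001 would give more. For VRE and composition the finding is mixing without a known direction. The primary safety and secondary efficacy results do not depend on these analyses.

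**What to change.** In SAP 6.8.2, 6.8.5 and 6.8.6:

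1. Flag each sample as before or after the first post-enema CDI anti-infective, fecal transplant or second enema, and show the two sets separately beside the all-sample display.
2. Show samples after a second enema in their own display, timed from that enema.
3. For C. difficile, add a display that counts a centrally confirmed recurrence as not cleared from its date onward.

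Medication changes, recurrence treatments and enema administration records are already collected (Protocol 7.3.3.2, 10.13 and 10.14), so no study procedure changes. The cost is SAP wording and one extra set of exploratory displays. The C. difficile figure in the third display will be lower. Pre-rescue displays at months 4 and 6 will describe mostly responders and must be labelled so. For that reason I would not make a pre-rescue-only display the main one for VRE or composition. The third display also partly repeats the secondary recurrence endpoint, which its footnote should say.

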6.9 Extent of Exposure to Study Treatment

The number and proportion of enemas (RBX2660) administered for each subject will be summarized using descriptive statistics. Time between study enema administrations will be summarized using descriptive statistics for both first and second enemas.

6.10 Subgroup Efficacy Analysis

The Chi-Square test will be used to assess the difference between the following additional subgroups:

- Subjects with immunocompromising conditions vs. Subject without immunocompromising conditions;
- Subjects with inflammatory bowel disease vs. Subject without inflammatory bowel disease at time of IP administration.

Note: Inflammatory bowel disease includes a medical history with PT term “Ulcerative colitis”, “Crohn's disease”, or “Inflammatory bowel disease”.

7 STATISTICAL METHODS

7.1 General Methodology

Data will be summarized using descriptive statistics with SAS® Version 9.3 or higher. Confidence intervals (CI) will be constructed at the level of 95% unless specified otherwise. For continuous variables, descriptive statistics (number of subjects [N], mean, standard deviation [SD], median, inter-quartile range [IQR], minimum, and maximum) will be generated. For discrete/categorical variables, the number and percentage of non-missing subjects will be generated. Standard operating procedures (SOPs) will be followed in the creation, validation and quality control of all data displays and analyses.

Subject listings of all data from the eCRFs as well as any derived variables will be presented.

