the Baseline visit (enema administration) and it will be collected and reviewed at the 1-week follow-up visit.

Subjects may receive a second RBX2660 enema if they are deemed failures following treatment per the protocol-specified treatment failure definition. This second enema is to be administered within 21 calendar days of failure determination. If a subject receives a second RBX2660 enema, the follow-up is completed via telephone assessments at 1-week, 4-week, 8-weeks, and 6-months after completing the second enema. A final analysis and report will be completed once the last subject has completed the 6-month follow-up visit for their study treatment, including 6-month follow-up after a second RBX2660 study treatment, if applicable.

3.1.1 ***Treatment Success***

Treatment success is defined as:

- The absence of CDI diarrhea through 8 weeks after completing a study treatment.

3.1.2 ***Sustained Clinical Response***

Sustained clinical response is defined as:

- Treatment success of the presenting CDI recurrence and no new CDI episodes through 6 months after completing a study treatment.

3.1.3 ***Treatment Failure***

Treatment failure (CDI recurrence) is defined as:

- The presence of CDI diarrhea within 8 weeks of administration of a study enema, which includes a positive stool test for *C. difficile* as determined by the central laboratory.

To ensure consistency across clinical sites for the determination of study failure, the central laboratory will perform the required C. DIFF QUIK CHEK COMPLETE® Test (QCC Test) rapid enzyme immunoassay test for glutamate dehydrogenase (GDH) and toxins A and B.

In the case of suspected treatment failure where there is an immediate concern for subject safety, including the potential for serious adverse events, a test may be conducted at the site or other laboratory known to the site **in addition to** sending a sample to the central laboratory for testing. In the event, the test results from the central laboratory differ from that of a local laboratory, the results from the central laboratory will be used in determination of treatment failure and eligibility to receive a second treatment with RBX2660.

3.1.4 ***Definition of Indeterminate Treatment Outcome***

If neither the protocol-specified definition for Treatment Success nor Treatment Failure is met, the treatment outcome will be considered Indeterminate.

3.1.5 ***Determination of Treatment Outcome***

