5.3 Analysis Populations

5.3.1 *Safety Population*

The safety population (SP) is defined as the population of subjects who had any treatment attempted or completed. The safety population will be used in analysis of all safety endpoints including the primary endpoint.

5.3.2 *Intent-to-Treat Population*

The ITT population is defined as all subjects enrolled, excluding screen failures.

5.3.3 *Modified Intent-to-Treat Population*

Analysis of the efficacy endpoints will use the modified Intent-to-Treat (mITT) population as a primary efficacy analysis population. The mITT population is defined as all subjects who successfully received treatment but excluding:

- subjects in whom treatment was attempted but not completed and;
- subjects who discontinue from the study prior to evaluation of treatment failure/success for the 8-week efficacy endpoint if the reason for exit is not related to CDI symptoms. Reason for exit will be

captured on the exit form to allow for identification of such subjects. Examples of reasons unrelated to CDI symptoms may include:

- Withdrawal of consent
- Death unrelated to CDI

5.3.4 *Per-Protocol Population*

The per-protocol (PP) population will consist of all subjects who successfully received treatment analyzed according to the treatment they received, excluding:

- Subjects who have documented protocol deviations to inclusion or exclusion criteria.
- Subjects who exited prior to the 8-week efficacy evaluation if the reason for exit was not related to CDI symptoms in the same manner as the mITT population.

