6.7.1.1 Treatment Success

Assessment of secondary efficacy objectives will include descriptive statistics and will be performed on the mITT population. Additional sub-analyses of safety data may be performed on sub-populations.

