6.7.1.2 Sensitivity Analysis for the Efficacy Endpoints

The efficacy analyses will be repeated using the ITT and PP population to assess the sensitivity of the endpoints. The ITT analysis will serve as the conservative analysis as it considers all subjects who exit prior to the 8-week efficacy assessment as treatment failures regardless of treatment failure documentation.

Finally, the sensitivity of the efficacy endpoints will be assessed in a multivariate logistic regression adjusting for possible interactions of the following covariates: age (< 65 years, ≥ 65 years), sex (Female, Male), race group (White, Non-white), ethnicity (Hispanic-Latino, not Hispanic-Latino), site geography (outside the US, Eastern US*, Southern US*, Northern US*, Western US*), and categories of number of previous episodes of CDI recurrence at Baseline (≤ 3 , > 3). Comorbidities will also be reviewed for possible interactions. This analysis will be performed on all populations where at least 20 subjects are available in each sub-group.

*States included in the identified US geographical regions are as follows:

- Eastern US: Connecticut, Delaware, District of Columbia, Maine, Maryland, Massachusetts, New Hampshire, New Jersey, New York, Ohio, Pennsylvania, Rhode Island, Vermont, Virginia, West Virginia
- Southern US: Alabama, Arkansas, Georgia, Florida, Kansas, Kentucky, Louisiana, Mississippi, North Carolina, Oklahoma, South Carolina, Tennessee, Texas
- Northern US: Illinois, Indiana, Iowa, Michigan, Minnesota, Missouri, Nebraska, North Dakota, South Dakota, Wisconsin
- Western US: Arizona, California, Colorado, Idaho, Montana, Nevada, New Mexico, Oregon, Utah, Washington, Wyoming

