7.3 Handling of Dropouts or Missing Data

No imputations will be used in analyses/summaries. However, a LOCF analysis will be used for evaluation of the Cdiff32 scores. Missing safety data will not be imputed beyond the adjustments for adverse event data mentioned in **Section 6.4.3**.

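### The SAP does not say how mITT and PP count subjects who leave before week 8 because of CDI symptoms without a central-laboratory positive, and either reading of its rules gives a lower recurrence rate than counting them as failures

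*SAP*

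**What the plan says.** The main efficacy analysis uses mITT (SAP 6.7.1.1): "Assessment of secondary efficacy objectives will include descriptive statistics and will be performed on the mITT population". SAP 5.3.3 takes early leavers out of mITT when they discontinue before evaluation of the "8-week efficacy endpoint if the reason for exit is not related to CDI symptoms". SAP 5.3.4 does the same for PP: "Subjects who exited prior to the 8-week efficacy evaluation if the reason for exit was not related to CDI symptoms". A subject who leaves because of CDI symptoms therefore stays in both populations.

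Treatment failure requires CDI diarrhea and a positive central-laboratory stool test. If a local result disagrees, "the results from the central laboratory will be used in determination of treatment failure" (SAP 3.1.3). A subject who meets neither the success nor the failure definition is Indeterminate (SAP 3.1.4; Protocol 7.3.2). The Endpoint Adjudication Committee's determination is the one analysed (SAP 3.1.5).

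One rule turns early exit into failure, and SAP 6.7.1.2 gives it for the ITT sensitivity analysis: "it considers all subjects who exit prior to the 8-week efficacy assessment as treatment failures regardless of treatment failure documentation". No counterpart is given for mITT or PP.

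On denominators, SAP 7.1 says: "For discrete/categorical variables, the number and percentage of non-missing subjects will be generated". On missing data, SAP 7.3 says: "No imputations will be used in analyses/summaries". Its only exceptions are LOCF for the Cdiff32 scores and the adverse-event adjustments.

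**The concern.** The exclusion rule separates two kinds of early exit. Exits unrelated to CDI are treated as uninformative and removed. Exits related to CDI are kept, and the only sensible reason to keep them is that they carry information about the outcome. That purpose fails if the analysis then has no way to count them.

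A subject who goes home with symptoms and no central-laboratory result cannot be a success, because freedom from CDI diarrhea through week 8 was never observed. The subject cannot be a failure either, because the confirming test is absent. The ITT rule shows that the authors foresaw exits without documented failure, but the remedy stops at ITT.

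At stake is the 8-week recurrence rate in the population that the SAP names as primary for efficacy. The choice of coding would be made after open-label data are in hand. The logistic regression (SAP 6.7.1.2) and the subgroup chi-square tests (SAP 6.10) also need a two-level outcome, which Indeterminate does not supply.

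**Working it through.** The plan states no expected recurrence rate, exit rate or powering for this endpoint, so there is no planned figure to reproduce. The check compares three codings of the same subjects.

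**Inputs**
- N = 700 in mITT. Assumed; the cap is 750 treated (SAP 3.3).
- k = CDI-related exits before week 8 without an adjudicated success or failure. Not in the documents; assumed to be 1%, 3% or 5% of N, that is 7, 21 or 35.
- p = recurrence among classified subjects. Illustrative values: 100 − 78.9 = 21.1% (earlier open-label study, Protocol 5.3.3) and 100 − 70.4 = 29.6% (earlier Phase 3 study, Protocol 5.3.4).
- f = confirmed failures = p × (N − k), rounded.

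**Formulas for recurrence**
- Indeterminate treated as missing and dropped: f/(N − k)
- Indeterminate kept as a non-missing category: f/N
- Counted as failure: (f + k)/N

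The success rate is (N − k − f)/(N − k) if they are dropped, and (N − k − f)/N under both of the other codings.

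**Results (%)**

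| p | k | f | Recurrence, dropped | Recurrence, kept | Recurrence, failure | Success, dropped | Success, kept or failure |
|---|---|---|---|---|---|---|---|
| 21.1 | 7 | 146 | 21.1 | 20.9 | 21.9 | 78.9 | 78.1 |
| 21.1 | 21 | 143 | 21.1 | 20.4 | 23.4 | 78.9 | 76.6 |
| 21.1 | 35 | 140 | 21.1 | 20.0 | 25.0 | 78.9 | 75.0 |
| 29.6 | 7 | 205 | 29.6 | 29.3 | 30.3 | 70.4 | 69.7 |
| 29.6 | 21 | 201 | 29.6 | 28.7 | 31.7 | 70.4 | 68.3 |
| 29.6 | 35 | 197 | 29.6 | 28.1 | 33.1 | 70.4 | 66.9 |

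**Distance below failure coding**
- Dropped: (k/N)(1 − p). Smallest: 0.01 × (1 − 0.296) = 0.7 points. Largest: 0.05 × (1 − 0.211) = 3.9 points.
- Kept: exactly k/N, that is 1 to 5 points.

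For scale, the normal-approximation 95% interval for the dropped-case rate at k = 7 runs from 18.0% to 24.1% at p = 21.1%, and from 26.2% to 33.0% at p = 29.6%. The half-widths are about 3.1 and 3.4 points. At 5% exits the shift reaches or passes the half-width; at 1% to 3% it stays inside. The interval does not reflect the shift in either case. Setting N = 750 changes the rates by no more than about 0.1 to 0.2 points.

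**The case against.** A reader might infer that every subject who exits because of CDI symptoms lacks an outcome and is dropped. The documents do not support that. Suspected recurrence calls for an in-office visit and a stool sample sent to the central laboratory (Protocol 10.13). A subject with qualifying diarrhea and a positive result is a failure whether or not they leave later. Confirmed failures either may receive a second enema or stay on their original schedule (Protocol 7.5), and the committee adjudicates outcomes. Only unconfirmed exits are at issue, and they may be few.

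A reader might also infer that the success rate is necessarily too favourable. That follows only if Indeterminate is treated as missing, which the SAP nowhere says. If it is a non-missing category, success is the same as under failure coding (66.9% in both at p = 29.6%, k = 35). The recurrence rate is still lower, and recurrence within 8 weeks is how the endpoint is worded (SAP 5.5.1).

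Third, the plan already gives some visibility. SAP 6.1 identifies treated subjects who withdrew before the 8-week evaluation, with reasons, and the ITT analysis counts all early exits as failures. Both help. But ITT also counts exits unrelated to CDI as failures and takes in enrolled subjects who are outside mITT, so it bounds the effect without isolating this group.

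Finally, some unconfirmed exits will not be true recurrences: Protocol 11.3 lists increased diarrhea as an anticipated event that need not be caused by CDI. This stands. Failure coding is a conservative convention, and the distances above are distances from that convention, not from a known true rate.

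**Conclusion.** The gap is real but confined to CDI-related exits before week 8 without an adjudicated success or failure. The plan keeps these subjects in mITT and PP, gives no rule there that counts them, and states general rules that prevent their being counted as failures. Recurrence falls below failure coding on either reading; success rises above it on one reading only. How large the effect is depends wholly on an exit rate that the documents do not give, and the ranges shown hold only for the assumed exit share, population size and base recurrence rates.

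The endpoint is secondary and descriptive in a single-arm safety study, and no decision rule depends on it. The point is still worth correcting: it concerns the main efficacy analysis, the direction is favourable to the product, and the remedy extends a convention that the SAP already uses for ITT.

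**What to change.** In SAP 6.7.1.1 and 7.3, state that in mITT and PP a subject who exits before the 8-week evaluation for a reason related to CDI symptoms, without an adjudicated success or failure, is counted as a treatment failure, and that all subjects in the population form the denominator. Report the number of such subjects, and separately the number of other Indeterminate outcomes, beside the rate. In 7.3, list this rule and the ITT rule as exceptions to the no-imputation statement; read literally, that statement already conflicts with the ITT rule.

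The cost is a few sentences and one extra count in the efficacy table. The downside is a slightly less favourable rate that may include some exits that were not true recurrences. The reported counts let a reader recompute the rate under the other codings.
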